7.10 Concomitant Medications and Prophylactic Treatment

Patients cannot receive any standard or investigational treatment (except CPI-613) for their cancer, or any other investigational drugs for any indications, while on this study. All otherwise permitted concomitant medications (including trade and generic names, dosage and dosing schedule) must be recorded.

Prophylactic treatment for drug-related symptoms is not planned, or it will interfere with the assessment of the toxicity of the investigational product. However, following the evaluation of the causal relationship of the symptom(s) to the study drug and the information has been documented, the investigator may prescribe supportive treatment. Supportive treatment may include anti-emetic, anti-diarrhea, anti-pyretic, anti-allergic, anti-hypertensive medications, analgesics, antibiotics, allopurinol, and others such as blood products and bone marrow growth factors. Patients may use erythropoietin for chronic anemia. Also, the hemoglobin should be maintained ≥ 9 g/dL or ≥ 90 g/L during the course of the study. The treating physician may utilize erythropoietic factors, or blood or platelet transfusions at their discretion.

8.0 ADVERSE EVENTS LIST AND REPORTING REQUIREMENTS

8.1 Adverse Event Characteristics

- **CTCAE term (AE description) and grade:** The CTEP Active Version of the NCI Common Terminology Criteria for Adverse Events (CTCAE 4.0) will be utilized for AE reporting. The CTEP Active Version of the CTCAE is identified and located on the CTEP website at http://ctep.cancer.gov/protocolDevelopment/electronic_applications/ctc.htm. All appropriate treatment areas should have access to a copy of the CTEP Active Version of CTCAE.
- **‘Expectedness’:** AEs can be ‘Unexpected’ or ‘Expected’ (see Section 7.1 above) for expedited reporting purposes only.
- **Attribution of the AE:**
 - Definite – The AE *is clearly related* to the study treatment.
 - Probable – The AE *is likely related* to the study treatment.
 - Possible – The AE *may be related* to the study treatment.
 - Unlikely – The AE *is doubtfully related* to the study treatment.
 - Unrelated – The AE *is clearly NOT related* to the study treatment.

List of Adverse Events to be Reported:

Comprehensive Cancer Center of Wake Forest University
A Pilot Study: Open-Label Clinical Trial of CPI-613 in Patients with Advanced Bile Duct
Cancers
CCCWFU # 59212

*Abdominal pain
Alkaline phosphatase
ALT (SGPT)
Anorexia
AST (SGOT)
Bilirubin (hyperbilirubinemia)
Calcium (hypercalcemia, hypocalcemia)
*Creatinine
*Diarrhea
Flushing
Hemoglobin (anemia)
*Injection site Reaction
Leukocytes
Lymphopenia
*Nausea
Neutrophils (neutropenia)
Platelets (thrombocytopenia)
Potassium
Sodium
*Vomiting

All grade 3, 4, 5 adverse events should be reported on flowsheets and in ORIS regardless of whether they are on this list.

Asterisk (*) denotes expected Adverse Events.

All Serious Adverse Events (SAEs) which are Possibly, Probably or Definitely Related to CPI-613, and Unexpected are required to be reported to Cornerstone Pharmaceuticals via the provided SAE Reporting Form within 7 days. All completed forms must be sent to [name] at Cornerstone. Cornerstone will submit any applicable SAEs to the FDA.

SAE reports must be submitted to Cornerstone by fax or email to the following address:

Department of Regulatory and Clinical Affairs
Cornerstone Pharmaceuticals, Inc.
[name]
[name]
[contact]
Telefax: [contact] Email: [contact]

8.2 STRC SAE Reporting Requirements

The Safety and Toxicity Review Committee (STRC) is responsible for reviewing SAEs for CCCWFU Institutional studies as outlined in Appendix B. STRC

Comprehensive Cancer Center of Wake Forest University
A Pilot Study: Open-Label Clinical Trial of CPI-613 in Patients with Advanced Bile Duct
Cancers
CCCWFU # 59212

currently requires that all unexpected grade 4 and all grade 5 SAE's on these trials be reported to them for review. This procedure is a part of the CCCWFU Data Safety Monitoring Plan that our institution has on file at the NCI. All CRM staff members assisting a PI in investigating, documenting and reporting an SAE qualifying for STRC reporting are responsible for informing a clinical member of the STRC committee as well as the entire committee via the email notification procedure of the occurrence of an SAE.

8.3 WFUHS IRB AE Reporting Requirements

Any unanticipated problems involving risks to subjects or others and adverse events shall be promptly reported to the IRB, according to institutional policy. Reporting to the IRB is required regardless of the funding source, study sponsor, or whether the event involves an investigational or marketed drug, biologic or device. Reportable events are not limited to physical injury, but include psychological, economic and social harm. Reportable events may arise as a result of drugs, biological agents, devices, procedures or other interventions, or as a result of questionnaires, surveys, observations or other interactions with research subjects.

All members of the research team are responsible for the appropriate reporting to the IRB and other applicable parties of unanticipated problems involving risk to subjects or others. The Principal Investigator, however, is ultimately responsible for ensuring the prompt reporting of unanticipated problems involving risk to subjects or others to the IRB. The Principal Investigator is also responsible for ensuring that all reported unanticipated risks to subjects and others which they receive are reviewed to determine whether the report represents a change in the risks and/or benefits to study participants, and whether any changes in the informed consent, protocol or other study-related documents are required.

Any unanticipated problems involving risks to subjects or others occurring at a site where the study has been approved by the WFUHS IRB (internal events) must be reported to the WFUHS IRB within 7 calendar days of the investigator or other members of the study team becoming aware of the event.

Any unanticipated problems involving risks to subjects or others occurring at another site conducting the same study that has been approved by the WFUHS IRB (external events) must be reported to the WFUHS IRB within 7 calendar days of the investigator or other members of the study team becoming aware of the event.

Any event, incident, experience, or outcome that alters the risk versus potential benefit of the research and as a result warrants a substantive change in the research protocol or informed consent process/document in order to insure the

Comprehensive Cancer Center of Wake Forest University
A Pilot Study: Open-Label Clinical Trial of CPI-613 in Patients with Advanced Bile Duct
Cancers
CCCWFU # 59212

safety, rights or welfare of research subjects.

9.0 STATISTICAL CONSIDERATIONS

This is a pilot study with the primary goal to be able to determine initial estimates of RR, and secondary goals to determine PFS and OS. Data from this trial will also provide additional data concerning the safety profile of the CPI-613 therapy. Since there is some uncertainty about what dose to examine for the 10 patients in this pilot study we propose the following pre-defined dose escalation scheme in order to determine the appropriate dose to provide to 10 patients with advanced bile duct cancers. This scheme has been discussed/proposed by the FDA and it is very specific and is described below. The dose-escalation scheme is based on the number of patients exhibiting dose-limiting toxicity (DLT), and DLT is defined as toxicity of Grade 3 or higher. The DLT determining period for all cohorts in the dose-escalation scheme is through the first cycle. Note – this section is redundant with section 6.1 but is included for completeness.

Cohort 1: The first 3 patients will not be treated with the 5 daily doses of CPI-613 during the pre-Cycle 1 week, and will only be treated with 3-weeks-on-1-week-off treatment cycles (see Table 6-1). The dose of CPI-613 will be 2,300 mg/m² (which is approximately three-quarters of the target dose). If none of these 3 patients develop a dose-limiting toxicity (DLT) through Cycle 1, the dose for the 3-weeks-on-1-week-off treatment cycles will be 3,000 mg/m² in all subsequent patients in this trial. However, if a DLT is observed in a patient (whether it is the 1st, 2nd or 3rd of the 3 intended patients), the number of patients in this cohort will be expanded to a maximum of 6 patients. If no DLT is observed in another patient out of a maximum of 6 patients, the dose for the 3-weeks-on-1-week-off treatment cycles will be 3,000 mg/m² in all subsequent patients in this trial. However, once DLT is observed in 2 patients, no additional patients will be treated at 2,300 mg/m² for the 3-weeks-on-1-week-off treatment cycles from that point on, even though the total number of patients in this cohort is as few as 2. The dose level of 2,300 mg/m², which induces a DLT in 2 or more patients, is considered to be above the maximum tolerated dose (MTD) for the 3-weeks-on-1-week-off treatment cycles. In this case, all subsequent patients in this trial will be treated at 1,700 mg/m² for the 3-weeks-on-1-week-off treatment cycles.

Cohort 2: In another 3 patients, the dose of CPI-613 for the 3-weeks-on-1-week-off treatment cycles will be as determined from Cohort 1. These patients will also be treated with the 5 daily doses of CPI-613 during the pre-Cycle 1 week. The dose of CPI-613 for the pre-Cycle 1 week will be 1,200 mg/m²/day, which has previously been established to be the weekly MTD (see Section 6.1.2). If none of these 3 patients develop a DLT, the study can move onto Cohort 3.

However, if a DLT is observed in a patient (whether it is the 1st, 2nd or 3rd of the 3 intended patients), the number of patients in this cohort will be expanded to a maximum of 6 patients. If no DLT is observed in another patient out of a maximum of 6 patients, the study will move onto Sub-Cohort 2 (see below). However, if a DLT is observed in 2 patients, no additional patients will be treated at 1,200 mg/m²/day during the pre-Cycle 1 week even though the total number of patients at this cohort is as few as 2. The dose level of 1,200 mg/m²/day during the pre-Cycle 1 week, which induces a DLT in 2 or more patients, is considered to be above the MTD for the

Comprehensive Cancer Center of Wake Forest University
A Pilot Study: Open-Label Clinical Trial of CPI-613 in Patients with Advanced Bile Duct
Cancers
CCCWFU # 59212

pre-Cycle 1 week. In this case, the dose of CPI-613 for the pre-Cycle 1 week in subsequent patients in this trial will be 600 mg/m²/day (or 3,000 mg/m²/week, equivalent to the MTD when given as a single dose).

Sub-Cohort 2: Sub-Cohort 2 is activated only if 1 out of 6 patients exhibits DLT in Cohort 2. There are 3 patients in this sub-cohort, the dose of CPI-613 for the 3-weeks-on-1-week-off treatment cycles will be as determined from Cohort 1. These patients will also be treated with the 5 daily doses of CPI-613 during the pre-Cycle 1 week. The dose of CPI-613 for the pre-Cycle 1 week will be 1,700 mg/m²/day. If none of these 3 patients develop a DLT, the study can move onto Cohort 3. However, if a DLT is observed in a patient (whether it is the first, second or third of the 3 intended patients), the number of patients in this cohort will be expanded to a maximum of 6 patients. If no DLT is observed in another patient out of a maximum of 6 patients, the study will move onto Cohort 3. However, if a DLT is observed in 2 patients, no additional patients will be treated at 1,700 mg/m²/day during the pre-Cycle 1 week even though the total number of patients at this sub-cohort is as few as 2. The dose level of 1,700 mg/m²/day during the pre-Cycle 1 week, which induces a DLT in 2 or more patients, is considered to be above the MTD for the pre-Cycle 1 week. In this case, the dose of CPI-613 for the pre-Cycle 1 week in subsequent patients in this trial will be 600 mg/m²/day (or 3,000 mg/m²/week, equivalent to the MTD when given as a single dose).

Cohort 3: This cohort will be performed only if DLT is observed in Cohort 2, or DLT is observed in 1 or less patients in Sub-Cohort 2. There are 3 patients in this cohort, and the dose of CPI-613 for the 3-weeks-on-1-week-off treatment cycles will be as determined from Cohort 1. The dose for the 5 daily IV infusions during the pre-Cycle 1 week will be 2,300 mg/m²/day. If none of these 3 patients develop a DLT, the study can move onto Cohort 4. However, if a DLT is observed in a patient (whether it is the 1st, 2nd or 3rd of the 3 intended patients), the number of patients in this cohort will be expanded to a maximum of 6 patients. If no DLT is observed in another patient out of a maximum of 6 patients, the study will move onto Cohort 4. However, if a DLT is observed in 2 patients, no additional patients will be treated at 2,300 mg/m²/day during the pre-Cycle 1 week even though the total number of patients at this sub-cohort is as few as 2. The dose level of 2,300 mg/m²/day during the pre-Cycle 1 week, which induces a DLT in 2 or more patients, is considered to be above the MTD for the pre-Cycle 1 week. In this case, the dose of CPI-613 for the pre-Cycle 1 week in subsequent patients in this trial will be 1,700 mg/m²/day.

Cohort 4: This cohort will be performed only if DLT is observed in 1 or less patients in Cohort 3. There are 3 patients in this cohort, and the dose of CPI-613 for the 3-weeks-on-1-week-off treatment cycles will be as determined from Cohort 1. The dose for the 5 daily IV infusions during the pre-Cycle 1 week will be 3,000 mg/m²/day. If none of these 3 patients develop a DLT, the study can move onto Cohort 5. However, if a DLT is observed in a patient (whether it is the first, second or third of the 3 intended patients), the number of patients in this cohort will be expanded to a maximum of 6 patients. If no DLT is observed in another patient out of a maximum of 6 patients, the study will move onto Cohort 5. However, if a DLT is observed in 2 patients, no additional patients will be treated at 3,000 mg/m²/day during the pre-Cycle 1 week

Comprehensive Cancer Center of Wake Forest University
A Pilot Study: Open-Label Clinical Trial of CPI-613 in Patients with Advanced Bile Duct
Cancers
CCCWFU # 59212

even though the total number of patients at this cohort is as few as 2. The dose level of 3,000 mg/m²/day during the pre-Cycle 1 week, which induces a DLT in 2 or more patients, is considered to be above the MTD for the pre-Cycle 1 week. In this case, the dose of CPI-613 for the pre-Cycle 1 week in subsequent patients in this trial will be 2,300 mg/m²/day

Cohort 5: This cohort is performed once the dose of CPI-613 for the 3-weeks-on-1-week-off treatment cycles has been determined from Cohort 1, and once the dose of CPI-613 for the pre-Cycle 1 week has been determined from Cohort 2-4. There are 10 patients in this cohort. These patients will be treated with CPI-613 for 5 days during the pre-Cycle 1 week at doses as determined from Cohorts 2-4, and the dose of CPI-613 for the 3-weeks-on-1-week-off treatment cycles will be as determined from Cohort 1.

As can be seen by the above scheme there are several possible scenarios that could occur in order to determine the dose for the 10 patients to be evaluated in the pilot trial. Once the above procedure is completed we will then enroll 10 patients at the determined dose.

Accrual Rate

We anticipate accruing one patient per month for this protocol. Since the dose escalation procedure described above may involve a variable number of patients (at least 6 but possibly more) we cannot be certain the entire length of accrual for this protocol. However, we do anticipate that the total number of patients in this protocol will be between 16-40 (with 16-22 being the most likely range). Thus, we anticipate that we will reach the target sample size of 10 patients treated at MTD within two years. A minimum of 16 patients to a maximum of 40 patients will be accrued to the study, with the first 6-30 being evaluated for toxicity in a dose-escalated manner for determining the MTD, and the remaining 10 used in the analytic sample.

Proposed Analyses

The analyses for this protocol will be primarily descriptive. With a sample size of 10 treated at MTD, we do not expect to see statistically significant effects for the outcomes of interest, however this data will provide useful preliminary data on the overall safety and efficacy of CPI-613 and provide useful data to predict the variability and likely effect sizes for these outcomes.

For the time-to-event outcomes we will estimate survival curves for OS and PFS using Kaplan-Meier techniques. In addition, we will estimate the 6 month and 1-year OS and PFS rates for these participants. For response rate we will present the proportion of patients who are CR, PR, SD or PD. In addition, we will estimate the proportion of responders as the percent of patients who are CR or PR. For this rate we will also include a 95% confidence interval.

We will also examine toxicities for these 10 patients by looking at each toxicity identified earlier in the protocol by grade.

Sample Size Considerations

Since this is a pilot study we do not anticipate having statistical power to detect specific effects, however with this sample size we will be able to estimate the response rate using a 2-sided 95% confidence interval with an interval that will extend no more than 0.31 from the observed

Comprehensive Cancer Center of Wake Forest University
A Pilot Study: Open-Label Clinical Trial of CPI-613 in Patients with Advanced Bile Duct
Cancers
CCCWFU # 59212

response rate.

Comprehensive Cancer Center of Wake Forest University
A Pilot Study: Open-Label Clinical Trial of CPI-613 in Patients with Advanced Bile Duct
Cancers
CCCWFU # 59212

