Cohort 2: In another 3 patients, the dose of CPI-613 for the 3-weeks-on-1-week-off treatment cycles will be as determined from Cohort 1. These patients will also be treated with the 5 daily doses of CPI-613 during the pre-Cycle 1 week. The dose of CPI-613 for the pre-Cycle 1 week will be 1,200 mg/m²/day, which has previously been established to be the weekly MTD (see Section 6.1.2). If none of these 3 patients develop a DLT, the study can move onto Cohort 3.

However, if a DLT is observed in a patient (whether it is the 1st, 2nd or 3rd of the 3 intended patients), the number of patients in this cohort will be expanded to a maximum of 6 patients. If no DLT is observed in another patient out of a maximum of 6 patients, the study will move onto Sub-Cohort 2 (see below). However, if a DLT is observed in 2 patients, no additional patients will be treated at 1,200 mg/m²/day during the pre-Cycle 1 week even though the total number of patients at this cohort is as few as 2. The dose level of 1,200 mg/m²/day during the pre-Cycle 1 week, which induces a DLT in 2 or more patients, is considered to be above the MTD for the pre-Cycle 1 week. In this case, the dose of CPI-613 for the pre-Cycle 1 week in subsequent patients in this trial will be 600 mg/m²/day (or 3,000 mg/m²/week, equivalent to the MTD when given as a single dose).

Sub-Cohort 2: Sub-Cohort 2 is activated only if 1 out of 6 patients exhibits DLT in Cohort 2. There are 3 patients in this sub-cohort, the dose of CPI-613 for the 3-weeks-on-1-week-off treatment cycles will be as determined from Cohort 1. These patients will also be treated with the 5 daily doses of CPI-613

Comprehensive Cancer Center of Wake Forest University
A Pilot Study: Open-Label Clinical Trial of CPI-613 in Patients with Advanced Bile Duct
Cancers
CCCWFU # 59212

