during the pre-Cycle 1 week. The dose of CPI-613 for the pre-Cycle 1 week will be 1,700 mg/m²/day. If none of these 3 patients develop a DLT, the study can move onto Cohort 3. However, if a DLT is observed in a patient (whether it is the first, second or third of the 3 intended patients), the number of patients in this cohort will be expanded to a maximum of 6 patients. If no DLT is observed in another patient out of a maximum of 6 patients, the study will move onto Cohort 3. However, if a DLT is observed in 2 patients, no additional patients will be treated at 1,700 mg/m²/day during the pre-Cycle 1 week even though the total number of patients at this sub-cohort is as few as 2. The dose level of 1,700 mg/m²/day during the pre-Cycle 1 week, which induces a DLT in 2 or more patients, is considered to be above the MTD for the pre-Cycle 1 week. In this case, the dose of CPI-613 for the pre-Cycle 1 week in subsequent patients in this trial will be 600 mg/m²/day (or 3,000 mg/m²/week, equivalent to the MTD when given as a single dose).

Cohort 3: This cohort will be performed only if DLT is observed in Cohort 2, or DLT is observed in 1 or less patients in Sub-Cohort 2. There are 3 patients in this cohort, and the dose of CPI-613 for the 3-weeks-on-1-week-off treatment cycles will be as determined from Cohort 1. The dose for the 5 daily IV infusions during the pre-Cycle 1 week will be 2,300 mg/m²/day. If none of these 3 patients develop a DLT, the study can move onto Cohort 4. However, if a DLT is observed in a patient (whether it is the 1st, 2nd or 3rd of the 3 intended patients), the number of patients in this cohort will be expanded to a maximum of 6 patients. If no DLT is observed in another patient out of a maximum of 6 patients, the study will move onto Cohort 4. However, if a DLT is observed in 2 patients, no additional patients will be treated at 2,300 mg/m²/day during the pre-Cycle 1 week even though the total number of patients at this sub-cohort is as few as 2. The dose level of 2,300 mg/m²/day during the pre-Cycle 1 week, which induces a DLT in 2 or more patients, is considered to be above the MTD for the pre-Cycle 1 week. In this case, the dose of CPI-613 for the pre-Cycle 1 week in subsequent patients in this trial will be 1,700 mg/m²/day.

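### The Cohort 2 and Cohort 3 clauses conflict, so a DLT-free trial has 22 or 16 patients; the stated minimum of 16 is 14 under the plan's own stopping rule

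*Combined protocol and SAP*

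**What the plan says.** Section 9.0, Accrual Rate, gives the enrolment bounds: "A minimum of 16 patients to a maximum of 40 patients will be accrued to the study, with the first 6-30 being evaluated" for toxicity and the remaining 10 forming the analytic sample. It says the escalation "may involve a variable number of patients (at least 6 but possibly more". It puts the likeliest total at 16 to 22, assumes one patient per month, and expects ten patients at the MTD within two years.

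The scheme behind those figures appears in Section 6.1.1 and again in Section 9.0, which says of itself that "this section is redundant with section 6.1 but is included for completeness". Three rules matter here.

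- Closing a cohort. Cohort 1 takes no more patients at its dose once two have a DLT, "even though the total number of patients in this cohort is as few as 2". Cohort 2 has the same rule, "even though the total number of patients at this cohort is as few as 2". Each then fixes a lower dose for later patients.
- Leaving Cohort 2 without a DLT: "If none of these 3 patients develop a DLT, the study can move onto Cohort 3".
- Entry to the third cohort is conditional: "This cohort will be performed only if DLT is observed in Cohort 2, or DLT is observed in 1 or less patients" (the second branch counts DLTs in Sub-Cohort 2). Section 9.0 repeats it: "This cohort will be performed only if DLT is observed in Cohort 2".

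Sub-Cohort 2 opens only after one DLT in six patients in Cohort 2. Section 9.0, Sample Size Considerations, says a two-sided 95% interval for the response rate will reach no more than 0.31 from the observed rate. No interval method is named there or under Proposed Analyses.

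**The concern.** After a Cohort 2 with no DLT, Sub-Cohort 2 is not activated, so neither branch of the Cohort 3 entry condition is met. One clause lets the trial go to Cohort 3 and the other forbids it. Because both sections carry both clauses, neither section settles the matter. The trial with no toxicity at all is therefore undetermined, and the forecasts of total enrolment and duration rest on a rule that the reader cannot identify.

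Separately, the lower enrolment bound looks as if it was counted without the two-DLT closing rule, while the upper bound uses the expansion rule in full. At stake is whether the planning figures can be checked against the scheme. The ten-patient analysis is not at stake.

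**Working it through.** **Inputs (Sections 6.1.1 and 9.0).** A cohort has 3 patients if none has a DLT. With one DLT it expands to at most 6. It closes at the second DLT. Two DLTs in Cohort 1 lead to Cohort 2, at the lower cycle dose the plan states. Two DLTs in Cohort 2, Sub-Cohort 2, 3 or 4 lead to Cohort 5 (10 patients). Accrual is 1 patient per month. The documents give no DLT rate, so every rate below is an assumption.

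**1. The plan's own bounds.** Maximum: five escalation cohorts of 6, so 5 × 6 = 30, and 30 + 10 = 40. This reproduces. The minimum of 16 reproduces only as two full cohorts: 3 + 3 + 10.

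**2. Minimum under the closing rule.** Cohort 1 closes at 2, Cohort 2 closes at 2, then Cohort 5: 2 + 2 + 10 = 14, with 4 in escalation. This path needs four DLTs in the first four patients, so its probability at a constant rate p is p⁴: 0.0001 at 10%, 0.0016 at 20%, 0.0081 at 30%. A total of 15 is also below the stated minimum. At p = 0.30:

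- P(cohort closes at 2) = 0.09
- P(closes at 3 with two DLTs) = 2 × 0.3 × 0.7 × 0.3 = 0.126
- P(0 of 3) = 0.343
- Cohort 2 clause: P(N<16) = 0.0081 + 0.09 × 0.126 + 0.469 × 0.09 = 0.062
- Cohort 3 clause: P(N<16) = 0.0081 + 2 × 0.09 × 0.469 = 0.093

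At 10% the two values are 0.008 and 0.015.

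**3. The DLT-free trial.** Cohort 2 clause: 3 + 3 + 3 + 3 + 10 = 22 patients, at least 22 months. Cohort 3 clause, taking Cohort 5 as the next step: 3 + 3 + 10 = 16 patients, at least 16 months. These are the two ends of the stated likely range.

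**4. Effect on the forecasts.** All paths were enumerated patient by patient at a constant DLT rate. N above 24 means more than two years at one patient per month.

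| Assumed DLT rate | 2% | 5% | 10% | 20% | 30% |
|---|---|---|---|---|---|
| P(N 16–22), Cohort 2 clause | 80% | 60% | 45% | 50% | 65% |
| P(N 16–22), Cohort 3 clause | 95% | 88% | 81% | 77% | 78% |
| P(N > 24), Cohort 2 clause | 20% | 38% | 48% | 37% | 19% |
| P(N > 24), Cohort 3 clause | 5% | 11% | 17% | 16% | 10% |

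Mean N at 10% is 24.1 under the Cohort 2 clause and 19.1 under the Cohort 3 clause. If rates rise over Cohorts 1, 2, Sub-2, 3 and 4 as 5/5/10/15/20%, P(N > 24) is 45% versus 11%.

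**5. Precision at n = 10.** Largest distance from the observed rate to a 95% limit:

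- Wald: 1.96 × √(0.25/10) = 0.3099, at 5/10
- Wilson: 0.5098 − 0.2 = 0.3098, at 2/10
- Clopper-Pearson: 0.5561 − 0.2 = 0.3561, at 2/10

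At 0/10 the upper limit is 0 (Wald), 0.28 (Wilson) or 0.31 (Clopper-Pearson).

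**The case against.** A reader might infer that the 16–22 range and the two-year forecast are wrong, or that no single rule could produce them. The documents do not support that. Under the Cohort 3 clause the range holds 77–95% of outcomes at the rates tabulated, and 16 is the most likely total at each of them. Under the Cohort 2 clause 22 is the most likely total at rates up to 20%. A total of 24 or fewer is more likely than not at every tabulated rate under both clauses (lowest 52%, at 10% under the Cohort 2 clause). The plan also says it cannot be certain how long accrual will last. What stands is narrower: the clauses contradict each other, and the plan does not say which one the forecasts assume.

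On the minimum, it can be said that the Cohort 3 entry text lets any DLT in Cohort 2, even two, open Cohort 3. The smallest trial would then be 2 + 3 + 10 = 15, with a DLT-free Cohort 2 going to Cohort 5. That reading strains the Cohort 2 closing text, which fixes the pre-Cycle 1 dose for later patients, and 15 still contradicts 16. It is also fair that the error is two patients, on a rare path, in a figure no analysis uses.

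Reconciling the clauses will not by itself make the forecast verifiable. No DLT rate is given, and the DLT definitions differ: Section 6.1.1 requires probable or definite attribution to CPI-613, while Section 9.0 names only the grade.

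A reader might also infer that 0.31 is wrong. It is not: two standard intervals give it, and the plan never says it will use an exact one.

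**Conclusion.** Two minor faults hold.

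The weightier one is the contradiction between the Cohort 2 and Cohort 3 clauses, present within both Section 6.1.1 and Section 9.0. It moves the DLT-free total between 22 and 16. At assumed constant DLT rates of 2–30%, the share of outcomes inside 16–22 is 45–80% under one clause and 77–95% under the other, and the chance of exceeding 24 patients is 19–48% versus 5–17%. These figures depend on the assumed rates and on Cohort 5 directly following a DLT-free Cohort 2 under the Cohort 3 clause. The contradiction does not depend on them.

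The lesser one is the minimum: 14 patients (4 in escalation), not 16 (6). This follows by counting from the closing rule. The maximum of 40 (30) is correct.

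The unnamed interval method is a missing detail, not an error.

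**What to change.** 1. Reconcile the Cohort 2 exit clause with the Cohort 3 entry clause, in Section 6.1.1 and Section 9.0 alike. This review takes no view on which should stand. Then restate the likely total and accrual time under the reconciled rule, with the assumed DLT rate. At one patient per month the maximum of 40 takes at least 40 months; any total takes longer if enrolment waits for the DLT period between cohorts.
2. After that, recount the minimum. With the closing rule as written, Accrual Rate should read 14–40 patients, 4–30 in escalation, and at least 4 instead of at least 6.
3. As a clarification, name the method for the response-rate interval. A Wald or Wilson interval keeps 0.31; Clopper-Pearson would need 0.36. Wald collapses to a single point at 0/10.

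The cost is wording in two sections and possibly less favourable planning figures. The ten-patient analytic sample does not change. The number of escalation patients depends on which clause is kept.
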